### 3.1 Sample Size Considerations

Other important treatments for HER2-positive MBC include T-DM1, lapatinib-capecitabine combination, and neratinib. Published ORRs reported for these regimens are 43.6%, 30.8%, and 24%, respectively [1-3]. The purpose of this study is to evaluate the safety and efficacy of poziotinib and identify the optimal dose for future clinical development.

The original protocol included test of hypotheses with a sample size of 70 as described below. For the primary endpoint of **ORR** in a single-arm study, to test the null hypothesis (hypothesis of no interest in the study) of 24% ( $P_0=0.24$ ) vs. the alternative hypothesis (hypothesis of interest in the study) of 42% ( $P_1=0.42$ ), a sample size of 70 patients achieves 88% power to detect a difference ( $P_1-P_0$ ) of 0.18 using a two sided binomial test. The target significance level is 0.05. The actual significance level achieved by this test is 0.0345. These results assume that the population proportion under the null hypothesis is  $P_0=0.24$ .

In Amendment 1, two lower dose cohorts were added to determine the optimal dose regimen. The test of hypotheses was removed, and the study became a proof-of-concept study. A

sample size of 30 was proposed for **Cohort 2**. If **Cohort 2** was stopped due to toxicity, a sample size of 20 patients was proposed for **Cohort 3**.

### 3.2 Randomization

This study is not randomized. Patients will be enrolled sequentially. The enrollment of Cohort 2 starts after enrollment of Cohort 1 is complete.

### 3.3 Tumor Assessments

Tumor assessment must be performed by Investigators using computed tomography (CT) or magnetic resonance imaging (MRI) at **Screening** up to 30 days prior to **Cycle 1, Day 1**. Imaging studies performed prior to the signing of Informed Consent as part of the site's routine standard of practice are allowed at the discretion of the Sponsor.

Tumor assessments will be performed every 6 weeks ( $\pm 14$  days) until disease progression, death, intolerable adverse events, or for up to 24 months.

Each subsequent tumor assessments must use the same Baseline radiologic technique, either CT or MRI. Response evaluation will be performed using RECIST criteria, Version 1.1 [4]. For radiographic assessment, CT or MRI must be performed at every assessment.

Measurable and non-measurable lesions that will not be followed by radiological methods should be documented appropriately.

#### 3.3.1 Baseline Tumor Assessments

Tumor assessment and measurement at baseline as well as post-baseline will follow the RECIST v1.1 criteria and will be evaluated by the local Principal Investigators. At Baseline tumor assessment, up to 5 measurable lesions (maximum of 2 lesions per organ) representative of all involved organs will be identified as **target lesions**. Target non-nodal tumor lesions (TLs) should have longest diameter  $\geq 10$ mm and can be measured reproducibly. Target lymph nodes (LNs) should have short axis  $\geq 15$ mm. The sum of diameters (SOD), which is the sum of the longest diameter of all target TLs and the short axis of all target LNs, will be calculated as the reference baseline value for tumor response evaluation later in the study.

All the other TLs, pathological LNs (short axis  $\geq 10$ mm), and lesions not measurable by CT or MRI will be identified as **non-target lesions** and the size of these lesions are not recorded for the purpose of follow-up.

#### 3.3.2 Follow-up Tumor Assessments

**Target lesions** are followed by tumor size, longest diameter of TLs and short axis of LNs, and SOD are calculated for response evaluation. At each tumor assessment, the tumor response of **target lesions** is determined as below.

- **Complete Response (CR):** disappearance of all target TLs and all target LNs with short axis <10mm
- **Partial Response (PR):**  $\geq 30\%$  decrease in SOD from **Baseline**, and not PD (see below)
- **Progressive Disease (PD):**  $\geq 20\%$  increase in SOD from previous smallest SOD on study, and an absolute increase of  $\geq 5\text{mm}$
- **Stable Disease (SD):** SOD change neither sufficient for PR nor sufficient for PD
- **Not Evaluable (NE):** not all target lesions evaluated, and evaluated lesions not sufficient for PD

**Non-target lesions** are assessed qualitatively with present, absent or unequivocal progression and tumor response is determined as below.

- **Complete Response (CR):** disappearance of all non-target TLs, normalization of tumor marker level, and all non-target LNs with short axis <10mm
- **Non-CR/Non-PD:** persistence of any non-target lesion and/or maintenance of abnormal tumor marker level
- **Progressive Disease (PD):** unequivocal progression (substantial worsening) of existing non-target lesions
- **Not Evaluable (NE):** not all non-target lesions evaluated
- **Not Applicable (NA):** no non-target lesions identified at **Baseline**

**New lesions** are tumor lesions that were not present at **Baseline**. The finding of a new lesion should be unequivocal, and the appearance of new malignant lesions denotes disease progression.

### 3.3.3 Time Point Response at Each Tumor Assessment

As summarized below, the time point response at each follow-up tumor assessment are determined according to the evaluation of target lesions, non-target lesions, and new lesions.

Table 1. Determination of Time Point Response

Target Lesions	Non-Target Lesions	New Lesions	Time Point Response
CR	CR or NA	No	CR
CR	Non-CR/Non-PD or NE	No	PR
PR	Any but PD	No	
SD	Any but PD	No	SD
PD	Any	Yes or No	PD
Any	PD	Yes or No	
Any	Any	Yes 	
NE	Any but PD	No	NE

 If the finding of new lesion is equivocal, it should be confirmed from next scan.

#### 4 ANALYSIS POPULATIONS

Two analysis populations have been defined as follows:

- The **Evaluable Population (EP)** consists of all patients who are enrolled, complete at least one cycle of poziotinib treatment, and have at least one evaluable post-baseline tumor response evaluation using RECIST criteria, Version 1.1.
- The **Safety Analysis Population (SAF)** includes all patients who signed informed consent, enrolled, and received at least one dose of study treatment. All demographics, Baseline characteristics, and safety data will be analyzed using the **SAF** population.

#### 5 STATISTICAL METHODS OF ANALYSIS

##### 5.1 General Principles

The statistical analyses will be reported using summary tables, figures, and data listings. All analyses and tabulations will be performed using SAS® Version 9.3 or higher. All tables, listings, and figures will be validated and reviewed before being finalized.

In summary tables of continuous variables, the minimum and maximum will be presented to the same number of decimal places as the original data. The mean, median, and 95% confidence interval (CI) will be presented to one more decimal place than the original data. The standard deviation (SD) and standard error (SE) will be presented to two more decimal place than the original data.

In summary tables of categorical variables, count and percentage will be provided. In general, percentage values are to be presented to whole number if sample size  $\leq 100$ ; to one decimal place if sample size is between 100 and 1000; and to two decimal places if sample size is greater than 1000. Any test of comparison performed will be 2-sided at 5% level of significance unless otherwise specified.

##### 5.1.1 Definition of Baseline Values

Baseline values will be defined as the most recent non-missing measurements collected prior to the first dose of poziotinib. If there is more than one value on or before the date of the first dose of poziotinib, the values closest to and prior to (including on) the date of the first dose will be used as the baseline value. Change from baseline will be defined as post-baseline value minus baseline value.

##### 5.1.2 Handling of Missing Data

Missing data will be not imputed.

### **5.1.3 Pooling of Centers**

Data from different centers will be combined for the purpose of the analysis. The number of patients enrolled will be presented by study site.

### **5.1.4 Interim Analysis**

There will be no formal interim analysis specified or conducted in this study. The data will be periodically reviewed for quality and completion.

### **5.1.5 Testing/Validation Plan**

SAS® Version 9.3 or higher on the Windows system will be used for creation of Tables, Listings, and Figures. All tables, listings, and figures will be validated and reviewed before being finalized. Independent programming will be conducted to verify tables and listings as appropriate. Tables will be reviewed for accuracy, consistency with this plan, consistency within tables, and consistency with corresponding outputs.

## **5.2 Background Characteristics**

All background characteristics will be summarized by cohort and for all patients. Corresponding patient data listings will be provided.

### **5.2.1 Patient Disposition**

Disposition of patients will be summarized for all enrolled patients. The summary data will include number (%) of patients in SAF, in EP, and who completed the study (i.e., treatment for 24 months). The reasons for treatment discontinuation and study discontinuation will also be summarized.

### **5.2.2 Protocol Deviation**

The following important protocol deviations will be summarized with count and percentage.

- Patients entered the study even though they did not satisfy the entry criteria.
- Patients developed withdrawal criteria during the study but were not withdrawn.
- Patients received the wrong treatment or incorrect dose.
- Patients received an excluded concomitant treatment.

All protocol deviations will be provided in patient data listings.

### **5.2.3 Demographic and Baseline Characteristics**

Demographics and other baseline disease characteristics will be summarized using descriptive statistics. The summary will include, but will not be limited to, age (as continuous and categorical [ $<65$ ,  $\geq 65$  and  $<75$ ,  $\geq 75$ ]), gender, ethnicity, race, height, weight, body mass index,

ECOG performance status, staging, hormone receptor status, prior HER2 therapy and prior cancer therapy (surgery, radiation and chemotherapy).

#### **5.2.4 Medical History**

Medical history information will only be provided in patient data listings.

#### **5.2.5 Concomitant Medication**

A concomitant medication will be defined as any medication that was taken either on the day of or after the administration of the first dose of poziotinib through the end of the study. This includes medications that started prior to the initiation of the first dose of poziotinib if the patient continues using it.

For all concomitant medications, counts and percentages of patients will be presented by medication class and preferred name coded by the World Health Organization Drug dictionary (WHODrug Enhanced SEP-2015 B2). Patients with more than one medication of the same medication class or preferred name will be counted only once. Patient data listings will be provided.

### **5.3 Efficacy Analyses**

All efficacy endpoints will be analyzed based on the Evaluable Population for each cohort.

#### **5.3.1 Best Overall Response**

Since there is no statistical test of hypotheses in this proof-of-concept study, the overall responses will be provided using various criteria or assessment. The determination of time point overall response will be made by the local site investigator using RECIST criteria, Version 1.1. The determination of best overall response (BOR) will be summarized as below.

1. Per Investigator Assessment: BOR will be summarized as reported by the local investigator. This includes CR, PR, SD, PD or NE. Please note the following:
  - Spectrum will not cross-check or derive the responses based on tumor measurement or time point responses as all BOR will be as reported by the investigator.
  - Local Investigator may not report a CR or PR as confirmed or unconfirmed, or SD adjudicated based on the duration of treatment and will be reported as is.
2. Per Sponsor Derivation: Spectrum will use the detailed tumor data as reported on case report form such as tumor measurements, lesion assessment, duration of treatment, and confirmation scan to derive the time point response and BOR using RECIST criteria, Version 1.1.
  - Time point response will be determined as described in Section 3.3.2 and 3.3.3.
  - BOR with confirmation will be determined as described in Table 2 below.

- BOR without confirmation will not require a confirmation scan for CR/PR or  $\geq 6$  weeks on-treatment.
- If there is a time point with missing tumor measurement, but the time point response is available from site, this time point response will be used for determination of BOR regardless of missing tumor measurement.

Table 1. Determination of Confirmed Best Overall Response

Initial Best Response (can start at any visit)	Response at Subsequent Visit	Best Overall Response
CR	CR 	CR
PR	PR  or unconfirmed CR 	PR
PR	SD (not followed by CR/PR)	SD
SD	SD or unconfirmed CR/PR	SD
CR or PR or SD	PD	SD  or PD 
CR or PR or SD	NE (no additional evaluable visit)	SD  or NE 
PD	Any	PD
NE	NE (no additional evaluable visit)	NE

 Confirmation scan needs to be  $\geq 4$  weeks from previous scan, 1 intervening NE is allowed.

 Confirmation scan needs to be  $\geq 4$  weeks from previous scan, 1 intervening NE/SD is allowed.

 If initial CR/PR/SD is  $\geq 6$  weeks on-treatment.

 If initial CR/PR/SD is  $< 6$  weeks on-treatment.

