**Protocol Version/Date: Amendment 2/14 Jul 2017**

### Study Design Diagram

**SCHEDULE OF ASSESSMENTS AND PROCEDURES**

Assessment	Screening	Treatment Period a (Each Cycle=21 [±3] Days) up to 24 Months						End-of-Treatment Visit
		Cycle 1			Cycle 2		Cycle 3+	
	Day -30 to Day-1	Day 1	Day 8±1	Day 14±3	Day 1	Day 8±1	Day 1	35 (±5) Days After Last Dose b
Informed Consent	x							
Relevant Medical History	x							
Demographic Data	x							
Height and Weight	x	x			x		x	x
Physical examination c	x	x			x		x	x
Vital signs	x	x			x		x	x
ECOG Performance Status	x	x			x		x	x
Pregnancy test (urine) d	x							
Tumor Receptor Status (ER, PR, HER2) and Stage	x							
Tumor Assessment e	x						x	x
CBC with 5-part differential and platelets f	x	x f	x		x	x	x	x
Serum Chemistry g	x	x g			x		x	x
Cardiac Ejection Fraction h	x							x
PK Samples i		x		x i	x		x	
Dispense Poziotinib and Loperamide j		x			x		x	
Adverse event assessment	x k	x	x	x	x	x	x	x
Dispense and Collect Patient Diary		x	x		x	x	x	x
Concomitant medications review	x	x	x	x	x	x	x	x

- a) Each cycle is comprised of 21 days. **Day 1** of a new cycle is applicable to **Day 22** of the previous cycle, with a window period of ± 3 days. If a visit is delayed during 1 cycle, the subsequent schedules will be delayed sequentially.
- b) An **End-of-Treatment Visit** will be performed 35 (±5) days after the last dose of poziotinib. An End of Study page will be recorded at that time.
- c) A complete physical examination is required at **Screening, Day 1** of each Cycle, and at the **End-of-Treatment Visit**. Symptom-directed exams are required at other visits.
- d) Pregnancy test (urine β-HCG) in women of child-bearing potential.
- e) Tumor assessment will be performed at **Screening** and every 6 weeks (± 14 days) until disease progression, death, or intolerable adverse events, whichever comes earlier. Imaging studies performed prior to the signing of Informed Consent as part of the site’s routine standard of practice are allowed at the discretion of the Sponsor.

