### 5.3.8 End-of-Treatment Visit (35 $\pm$ 5] Days Post-Study Treatment)

The **End-of-Treatment Visit** is required 35 ( $\pm 5$ ) days after the last dose of poziotinib is administered. The following assessments are to be performed at this visit:

- Physical examination
- Vital signs
- ECOG Performance Status assessment
- Tumor assessment (unless the patient has documented disease progression or has undergone a tumor assessment within the previous 6 weeks)
- CBC with 5-part differential and platelets
- Serum biochemistry
- Echocardiogram or MUGA scan to evaluate cardiac ejection fraction
- Adverse event assessment
- Patient Diary Collection
- Concomitant medications

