### 8.5.2 Secondary Endpoints

- **Safety, including adverse events and pharmacokinetics**
  - **Safety and adverse events:** Safety will be assessed by reported/elicited AEs, laboratory assessments including hematology and biochemistry, vital signs, physical examination, and neurological examination. The assessment of treatment-emergent AEs (TEAEs) includes SAEs, AEs leading to study drug discontinuation, and AEs related to the study drug.
  - **Pharmacokinetics:** All patients will have blood samples drawn pre-dose and at 1 hour and 2 hours ( $\pm 15$  min) post-dose for sparse PK sampling on **Day 1** of **Cycles 1, 2, and 3** and pre-dose on **Day 14** ( $\pm 3$  days) of **Cycle 1 (Cohort 1 only)**. If consented, intensive PK samples will be drawn pre-dose and 30 minutes, 1, 1.5, 2, 3, 4, 6, and 24 hours post-dose on **Day 1** of **Cycle 1**. In addition, if a patient presents with a potentially drug-related SAE, PK samples may be collected during the clinic visit for PK analysis.
  - **PFS** is defined as the number of days from the treatment start date to the date of documented disease progression or death due to any cause. Disease progression will be determined by RECIST Version 1.1.
  - **DCR**, including CR, PR, and Stable Disease (SD), will be assessed using RECIST, version 1.1 and defined as the proportion of subjects who achieve CR, PR, and SD by the best response from the first dose of poziotinib to the end of study.
  - **TTP** is defined as the period of time from the first dose of study drug to tumor progression, which excludes death without tumor progression, by the end of study.

The secondary efficacy variables of **PFS**, **DCR**, and **TTP** will be analyzed descriptively, for each cohort.

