### 5.4.1 Drug Exposure

The extent of exposure to poziotinib will be summarized with descriptive statistics using the following parameters:

- Duration of treatment: number of days between first dose and last dose of poziotinib, inclusive (i.e. days difference between first dose and last dose +1).
- Number of cycles treated
- Days of treatment administered
- Relative dose intensity (RDI): the percentage of planned dose that each patient actually received during the study. The planned dose is defined as the dose that would be given if no doses were missed and no dose reductions were made for the number of cycles (28 days per cycle) for the duration of treatment regardless of the number of cycles actually administered. Thus,

$$RDI = 100 * \frac{\text{total dose administered}}{336 * \left[ \text{integer of } \left( \frac{\text{days difference between first dose and last dose}}{21} \right) + 1 \right]}$$

- Last dose level: the last dose is assumed to be the lowest dose level prescribed by investigator
- Number of dose reduction
- Number and percentage of patients with no reduction, or with dose reduction to 16mg (Cohort 1 only), 12mg, 10mg and 8mg.
- Study day of first dose reduction
- Study day and duration of first drug interruption

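### Does the undefined 6-week on-treatment cut in the confirmed best overall response table leave the disease control rate open?

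*SAP*

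**What the plan says.** SAP 5.3.1 gives best overall response (BOR) in three forms: as the investigator reported it, derived by the sponsor with confirmation, and derived by the sponsor without confirmation. The 6-week cut belongs to the second form only. In that table an initial CR, PR or SD followed by no further evaluable visit is SD from 6 weeks and NE below it; followed by progression, it is SD or PD at the same cut. The short side reads "If initial CR/PR/SD is $< 6$ weeks on-treatment". The form without confirmation drops the cut.

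The same section mentions time on treatment twice more. The sponsor's inputs include "duration of treatment, and confirmation scan to derive the time point response and BOR using RECIST criteria, Version 1.1". For the investigator form, the site may not give "SD adjudicated based on the duration of treatment and will be reported as is". The SAP defines duration of treatment only in 5.4.1 Drug Exposure, as the "number of days between first dose and last dose of poziotinib, inclusive".

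The protocol can produce a scan after dosing has ended:

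- Routine imaging runs "until disease progression, death, or intolerable adverse events, whichever comes earlier" (Schedule of Assessments, footnote e).
- Protocol 5.3.8 lists for the End-of-Treatment Visit "Tumor assessment (unless the patient has documented disease progression or has undergone a tumor assessment within the previous 6 weeks".
- Footnote b of the Schedule says of that visit: "An End of Study page will be recorded at that time".
- Protocol 8.5.2 judges disease control "by the best response from the first dose of poziotinib to the end of study".

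**The concern.** Two clocks look possible: calendar time from first dose to the scan, or time on drug, which the two mentions of treatment duration seem to support. A patient who stops early for toxicity, with no scan in the preceding 6 weeks, is imaged about five weeks after the last dose and then leaves the study. With no later scan, footnotes 3 and 4 decide the class. SD counts toward the disease control rate (DCR) and NE does not, while the patient stays in the denominator either way. The patients concerned are early stoppers, in a study that added lower-dose cohorts because of tolerability. If the clock were chosen after the data were seen, it could raise or lower a named secondary endpoint.

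**Working it through.** **Inputs**

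- Cut: 6 weeks = 42 days (SAP 5.3.1).
- Cycle: 21 days; Cohort 1 doses on 14 of them, Cohort 2 on all (Protocol 6.1.3).
- Evaluable Population: one completed cycle and one evaluable scan after baseline (SAP 4).
- End-of-Treatment Visit: 30 to 40 days after last dose, or sooner if new treatment begins (Protocol 4.3).
- Routine scans: every 6 weeks, ±14 days (SAP 3.3).
- Enrolled: 33 in Cohort 1 and 34 in Cohort 2 (SAP 3).

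**Day counts.** Let first dose be day 1, last dose day L, and the scan g days after last dose. Assume dosing on schedule, and that a Cohort 1 cycle is complete with last dose on day 14.

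- Calendar clock: E = (L + g) − 1.
- Time-on-drug clock (SAP 5.4.1): D = L.

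| Cohort | L before day 42 | E for g = 30 to 40 | D | Combinations with E ≥ 42 |
|---|---|---|---|---|
| 1 | 14, 22–35 (15 days) | 14+30−1 = 43 to 35+40−1 = 74 | 14–35 | 165 of 15 × 11 = 165 |
| 2 | 21–41 (21 days) | 21+30−1 = 50 to 41+40−1 = 80 | 21–41 | 231 of 21 × 11 = 231 |

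D reaches 42 in none of the 396 combinations. Inside the visit window the clocks therefore always disagree for these patients. At L = 42 they agree.

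**Limits of that result**

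- If the visit is brought forward for new therapy, E < 42 whenever g ≤ 42 − L. With L = 21 and a scan within 21 days, both clocks give NE.
- The scan is waived if one was done in the previous 6 weeks, and routine scans are allowed from day 29 (42 − 14 = 28 days elapsed).
- The clocks can also differ elsewhere. A Cohort 1 patient with last dose on day 35 and a single scan on day 43 has E = 42 (SD) but D = 35 (NE). A patient whose only evaluable scan is on day 30, with dosing to day 60, has E = 29 (NE) but D = 60 (SD), if D covers the whole treatment period.

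**Which clock the text means**

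- The footnote's subject is the initial response, so it times the scan at which that response was seen. Footnotes 1 and 2 of the same table are also intervals to a scan.
- The 6-week cut equals the 6-week imaging interval. On time on drug, the Cohort 1 patient above, who took every dose of two cycles and was scanned on time, would be NE. That is implausible as an intention.
- The 5.4.1 definition serves exposure summaries, and 5.3.1 does not refer to it.
- The protocol's DCR period starts at first dose and does not end at last dose.

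**Size.** If k patients are reclassified among n evaluable, the confirmed DCR moves by k/n. The documents do not give n or k.

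- k = 1: 1/34 = 2.9 points (all of Cohort 2 evaluable), 1/30 = 3.3, 1/20 = 5.0.
- Illustration with assumed n = 25 and k = 3: 18/25 = 72% (exact 95% CI 50.6–87.9) becomes 15/25 = 60% (38.7–78.9).

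**What cannot move.** An unconfirmed CR or PR is not a confirmed response on either clock, so confirmed ORR is fixed. Investigator BOR is taken as reported. The form without confirmation has no 6-week rule. PFS and TTP do not use BOR.

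**The case for a change.** The strongest case for a change is that the term has no definition, while the section that uses it names treatment duration twice, once as an input to this very derivation. The only definition of that phrase in the SAP is first to last dose. Two programmers could classify the same patient differently, and the independent programming in SAP 5.1.5 cannot settle what a word means. Defining the term would cost a clause and need no new data.

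The missing definition and the day counts inside the visit window stand. What does not stand is that the two readings are equally good: time on drug depends on carrying over a definition from the exposure section, and it misclassifies a fully dosed Cohort 1 patient. Nor does the split hold for every early stopper, since a visit brought forward can give NE on both clocks. The worry about choosing a favourable figure is limited because the sponsor-derived DCR without confirmation is reported beside the confirmed one. It already counts these patients and is a ceiling for the confirmed rate on either clock.

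An extra output row counting SD patients whose last dose came before day 42 would not recover the time-on-drug rate. A patient with SD on days 29 and 74 and last dose on day 35 is SD without any footnote, yet the row would include that patient.

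**Conclusion.** This is a gap that analysts fill sensibly. Reading the 6 weeks as first dose to scan is natural and fits the table, the imaging interval and the protocol's DCR period. A defining clause would only record that reading; it would be a minor clarification and would not alter the analysis. At most, one of three descriptive DCRs and its SD/NE/PD split could differ, by 2.9 to 5.0 points per patient for n between 34 and an assumed 20. Any larger figure rests on assumed counts of affected patients, and the documents do not show that there is even one. No hypothesis is tested, and the primary endpoint does not depend on the clock. No change to the plan follows.
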